## STATEMENT OF COMPLIANCE

The trial will be carried out in accordance with International Council on Harmonisation Good Clinical Practice (ICH GCP) and the following:

- United States (US) Code of Federal Regulations (CFR) applicable to clinical studies (45 CFR Part 46, 21 CFR Part 50, 21 CFR Part 56, 21 CFR Part 312, and/or 21 CFR Part 812).

National Institutes of Health (NIH)-funded investigators and clinical trial site staff who are responsible for the conduct, management, or oversight of NIH-funded clinical trials have completed Human Subjects Protection and ICH GCP Training.

The protocol, informed consent form(s), recruitment materials, and all participant materials will be submitted to the IRB for review and approval. Approval of both the protocol and the consent form(s) must be obtained before any participant is consented. Any amendment to the protocol will require review and approval by the IRB before the changes are implemented to the study. All changes to the consent form(s) will be IRB approved; a determination will be made regarding whether a new consent needs to be obtained from participants who provided consent, using a previously approved consent form.

## 1 PROTOCOL SUMMARY

### 1.1 SYNOPSIS

Title:	Theta-burst stimulation modulates criticality and cognitive control
Grant Number:	R00MH125021
Study Description:	In this study we test the hypotheses that critical brain dynamics depend on the balance of cortical excitation to inhibition and that sub-criticality impacts on subjective cognitive effort and cognitive control.
Objectives*:	Primary Objective: Test whether continuous and intermittent theta burst stimulation can alter critical dynamics, cognitive control, and cognitive effort relative to sham stimulation. Secondary Objectives: Test whether the effects of continuous and intermittent theta burst stimulation reflect alterations in the cortical excitation to inhibition balance.
Endpoints*:	Primary Endpoint: Long-range temporal correlations and avalanche branching statistics from EEG signals. Cognitive control performance. Cognitive effort discounting of rewards. Secondary Endpoints: N/A
Study Population:	We will recruit 60 healthy young adults (30 F and 30 M; all 18-45 years old), from the Rutgers University Community in New Brunswick and Piscataway, NJ.
Phase* or Stage:	N/A
Description of Sites/Facilities Enrolling Participants:	This single-site study will be conducted at Rutgers University in the Center for Advanced Human Brain Imaging Research. No research will be conducted overseas.
Description of Study Intervention/Experimental Manipulation:	The study will involve three sessions of within-subject, crossover, double-blind, sham-controlled continuous and intermittent theta burst stimulation delivered either at the right frontal eye field.
Study Duration*:	24 months
Participant Duration:	Participants will complete all components within 4 months of their first visit.

### 1.2 SCHEMA

### 1.3 SCHEDULE OF ACTIVITIES

	Pre-screening (Pre-consent)	Visit 1 Day 1	Visit 2 Day 63 ±52	Visit 3 Day 70 ±50	Visit 4 Day 77 ±50
Review Eligibility	X				
Informed Consent		X			
Demographics		X			
Clinical history		X			
TMS & MRI compatibility		X			
MRI and Resting State Scans		X			
Outcome Evaluation					
Cognitive control performance			X	X	X

	Pre-screening (Pre-consent)	Visit 1 Day 1	Visit 2 Day 63 ±52	Visit 3 Day 70 ±50	Visit 4 Day 77 ±50
Effort Discounting			X	X	X
Long-range temporal correlations			X	X	X
Avalanche branching statistics			X	X	X
Functional E/I balance			X	X	X

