#### Risks associated with participation in TMS experiments:

(1) Heating, induced voltages, and magnetic field effects. The action of the magnetic field on any implanted or worn metal in, on, or around the head poses a significant risk. Magnetic fields can move or dislodge metal, induce current in conductive metals, cause heating around metal components, and/or affect the operation of any metal device. Thus, it is crucial to screen participants for any irremovable metal in or around the head. Our health screening includes the relevant screening questions.

(2) Hearing changes. Movement of the TMS coil within its casing when current is passed through it produces an audible “click”. Though this click is often not perceived as loud due to the stapedial reflex, it can nevertheless reach 140 dB or more of sound pressure. This exceeds OSHA sound level limits and could produce changes in hearing levels if exposed repeatedly. Thus, we will require all participants to wear earplugs. In addition, we will exclude participants with potential hearing problems.

(3) Induced seizure: Though exceedingly rare even in patients with epilepsy, induction of a “generalized” seizure is the most severe adverse event associated with TMS. A seizure is an episode of excessive brain activity and stiff muscle activity (often referred to as a “convulsion” or “fit”). Seizure risk increases at high stimulator output intensities, at high frequencies of stimulation, with multiple repeated trains of

stimulation, with long durations of stimulation, with short inter-train-intervals, and when stimulating participants with reduced seizure thresholds. However, the risk of seizure induction is minimal to negligible if TMS parameters are kept within the prescribed consensus safety parameters (Rossi et al., 2009; Rossi et al. 2020), and participants are carefully screened for seizure risk. Indeed, over the past decade of experience in both clinical and research domains, this risk has been reduced to the order of one 1 in 89,000 cases (Rossi et al 2020).

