As noted above, the chief risk of TMS studies is seizure, yet this risk is significantly mitigated by well established, consensus guidelines with a proven track record for safe administration (Rossi et al. 2009; Rossi et al. 2020). Key methods for minimizing seizure risk include screening against risk factors among otherwise healthy young adult participants (e.g. epilepsy, history of brain trauma, the use of anti-depressants, etc.). Additionally, we will adhere closely to safety consensus guidelines as articulated by Rossi et al., which have a proven track record of safe administration. Nevertheless, as we cannot rule out seizure risk entirely, every experiment will be run by the PI ([name]) or highly-trained staff member and a second experimenter trained to respond quickly and effectively in the event of a seizure. All experimenters will be thoroughly trained, and closely familiar with the protocol for responding including securing the participant to preclude further harm, contacting emergency medical services, remaining with and reassuring the participant until emergency medical services arrive, and subsequently documenting and reporting the incident to our IRB.

For MRI, there are no known risks beyond interactions between metal and the magnetic field. Hence, all participants are extensively screened for implanted metal. Persons at primary or secondary risk based on an implanted object or medical device will be excluded according to MRF operating procedures. Moreover, no personnel are permitted in the scanner room with any metal on their person. As such, we do not anticipate any significant risk from the application of these procedures. In rare cases, a participant

will become anxious because of lying in an enclosed space. We will exclude participants who report a history of anxiety in enclosed spaces, and we will terminate the session of a participant who expresses anxiety about lying in the bore.

All participants will be able to stop the session at any time by squeezing a ball held in one hand. The ball activates a buzzer in the control room. There is also an intercom voice link with the control room that allows verbal communication between participant and experimenters.

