#### 5.2 EXCLUSION CRITERIA

An individual who meets any of the following criteria will be excluded from participation in this study:

1. Ongoing drug or alcohol abuse
2. Diagnosed psychiatric or mental illness
3. Currently taking psychoactive medication
4. Prior brain injury
5. Metal in body
6. History of seizures or diagnosis of epilepsy
7. Claustrophobia
8. Pregnant or possibly pregnant
9. Younger than 18 or older than 45
10. Use of medications which potentially lower the seizure threshold

Participants younger than 18 are excluded because there is evidence that cortical excitation to inhibition changes throughout childhood and adolescence and has been associated with an increase in critical dynamics with development (Smit et al. 2011). There is also evidence of increasing excitation to inhibition altering scale-free properties linked to critical dynamics in older adults relative to young adults (Voytek et al. 2015). We are restricting our study to young adults aged 18-45 to avoid any confounds associated with early development or cognitive aging.

Participants will be asked if they are pregnant or possibly pregnant and excluded from participation if they affirm either.

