#### 7.2 PARTICIPANT DISCONTINUATION/WITHDRAWAL FROM THE STUDY

Participants are free to withdraw from participation in the study at any time upon request.

An investigator may discontinue a participant from the study for the following reasons:

- Identification of brain abnormalities during the MRI scan
- Non-compliance with regards to cognitive task instructions
- Lost-to-follow up; unable to contact subject (see **Section 7.3, Lost to Follow-Up**)
- Any event or medical condition or situation occurs such that continued collection of follow-up study data would not be in the best interest of the participant or might require an additional treatment that would confound the interpretation of the study; With TMS an unlikely but possible medical condition would be onset of a seizure
- The participant meets an exclusion criterion (either newly developed or not previously recognized) that precludes further study participation

The reason for participant discontinuation or withdrawal from the study will be recorded on the Case Report Form (CRF). Subjects who sign the informed consent form and are randomized but do not receive the study intervention may be replaced. Subjects who sign the informed consent form, and are randomized and receive the study intervention, and subsequently withdraw, or are discontinued from the study, will be replaced.

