## 8 STUDY ASSESSMENTS AND PROCEDURES

### 8.1 ENDPOINT AND OTHER NON-SAFETY ASSESSMENTS

During the screening process, participants will be informed about basic inclusion / exclusion criteria after they first contact us, by email. We will then ask participants questions, by phone, on the MRI and TMS screening forms in detail and indicate whether they meet criteria or not. Although we will not yet ask participants to fill out these forms (i.e. no data will be recorded at this stage), we will ask them to confirm that they meet all criteria on the forms, prior to scheduling their first visit. Within two weeks of this confirmation, we will invite participants for their first session visit.

At the first visit, participants will complete the informed consent process and then be asked to fill out the screening forms, after giving consent. These data will include information about psychiatric or psychological history, presence or absence of metal in the body, history of physical trauma to the brain, current alcohol or drug abuse, current use of psychiatric medications, and use of other medications which may lower the seizure threshold. We will also collect basic demographic and handedness information.

Following the informed consent process the following data will be collected during the study.

- **Performance-based assessments:** Oculmotor task performance, decision-making task performance
- **Questionnaires:** The Need for Cognition Scale
- **Imaging assessments:** Using a 64-channel EEG system, we will record brain waves at the scalp throughout all procedures during the stimulation session. In the MRI scanner we will collect several types of scans. For the purposes of TMS neuro-navigation, we will collect T1 MPRAGE sequences, structural localizer scans, functional localizer scans, and a field map scan. We will also collect 10-12 minutes of resting state fMRI data. These data will be collected on a 3T MRI.

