#### 8.3.4 TIME PERIOD AND FREQUENCY FOR EVENT ASSESSMENT AND FOLLOW-UP

The occurrence of an adverse event (AE) or serious adverse event (SAE) may come to the attention of study personnel during study visits and interviews of a study participant presenting for medical care, or upon review by a study monitor.

All AEs, not otherwise precluded per the protocol, will be captured on the appropriate case report form (CRF). Information to be collected includes event description, time of onset, clinician's assessment of severity, relationship to study procedures (assessed only by those with the training and authority to make a diagnosis), and time of resolution/stabilization of the event. All AEs occurring while on study will be documented appropriately regardless of relationship. All AEs will be followed to adequate resolution.

Any medical or psychiatric condition that is present at the time that the participant is screened will be considered as baseline and not reported as an AE. However, if the study participant's condition deteriorates at any time during the study, it will be recorded as an AE.

Changes in the severity of an AE will be documented to allow an assessment of the duration of the event at each level of severity to be performed. Documentation of onset and duration of each episode will be maintained for AEs characterized as intermittent.

The Principal Investigator will record events with start dates occurring any time after informed consent is obtained until 7 (for non-serious AEs) or 30 days (for SAEs) after the last day of study participation. At each study visit, the investigator will inquire about the occurrence of AE/SAEs since the last visit. Events will be followed for outcome information until resolution or stabilization.

---

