#### 8.3.9 REPORTING OF PREGNANCY

If participants indicate during screening that there is a chance they may be pregnant, we supply and ask participants to take a pregnancy test to ensure that they are not pregnant. If they are pregnant they will be withdrawn from the study and all procedures (MRI, TMS) for safety reasons.

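### Exclusions that can change over time (medication, substance abuse, pregnancy) are checked only up to Visit 1, but stimulation is given at Visits 2 to 4, nominally 62 to 76 days later

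*Protocol*

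**What the plan says.** Section 5.2 excludes people for states that can change within weeks: current psychoactive medication, ongoing drug or alcohol abuse, pregnancy, and "Use of medications which potentially lower the seizure threshold".

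The checks on these states are placed as follows.

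- **Section 1.3.** Eligibility review is marked at pre-screening only. Clinical history and "TMS & MRI compatibility" are marked at Visit 1 only. The columns for Visits 2 to 4 contain outcome measures only.
- **Section 8.1.** "At the first visit, participants will complete the informed consent process and then be asked to fill out the screening forms". These forms cover alcohol and drug abuse, psychiatric medication and drugs that may lower the seizure threshold.
- **Section 8.3.9.** The pregnancy test is conditional and tied to screening: "If participants indicate during screening that there is a chance they may be pregnant", a test is supplied. A pregnant participant is withdrawn from both MRI and TMS for safety reasons.
- **Section 6.5** (Concomitant Therapy) is marked not applicable.

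Two provisions reach beyond Visit 1. Section 7.2 lists as a ground for discontinuation: "The participant meets an exclusion criterion (either newly developed or not previously recognized) that precludes further study participation". Section 8.3.4 states: "At each study visit, the investigator will inquire about the occurrence of AE/SAEs since the last visit".

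**The concern.** Section 2.3.1 calls the seizure risk minimal to negligible on two conditions: stimulation parameters stay within the consensus limits, and "participants are carefully screened for seizure risk". Section 2.3.3 repeats the second: "Key methods for minimizing seizure risk include screening against risk factors among otherwise healthy young adult participants", with antidepressant use among its examples. The parameter limits apply afresh at every session. The screening is done once and then ages until the last stimulation visit. A participant who starts an antidepressant after Visit 1 would meet an exclusion criterion, yet nothing in the plan would bring this to light before the coil is switched on. The same holds for a pregnancy that begins or is recognised after Visit 1.

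There is a smaller statistical side. The protocol itself treats drugs as acting on its outcome constructs: Section 2.2 cites atomoxetine as shifting critical dynamics, and Section 6.1.1 cites a zolpidem study of the functional E/I ratio. A drug started between sessions and not recorded adds within-person noise to the active-versus-sham comparisons in Section 9.4.2, chiefly the behavioural ones.

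**Working it through.** **1. Age of the screening at each stimulation visit.** Inputs are the visit days and windows in Section 1.3, with Visit 1 on Day 1. Gap = visit day − 1; range = (visit day ± window) − 1.

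| Visit | Day and window | Nominal gap (days) | Range (days) |
|---|---|---|---|
| 2 | 63 ± 52 | 63 − 1 = 62 | 10 to 114 |
| 3 | 70 ± 50 | 70 − 1 = 69 | 19 to 119 |
| 4 | 77 ± 50 | 77 − 1 = 76 | 26 to 126 |

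The synopsis requires all components within 4 months of the first visit, about 122 days, which trims the upper end for Visit 4. Section 4.1 separately allows the first stimulation from the day after the MR scan up to 113 days after it.

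**2. Sessions concerned.** Each of the 60 planned participants has two active sessions and one sham session (Sections 4.1 and 4.4).

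- Active sessions, for seizure risk: 60 × 2 = 120.
- TMS visits by women, for the pregnancy exclusion: 30 × 3 = 90.

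These count the visits at which the re-check is missing. They are not numbers of people affected, because the protocol gives no rate of change for any of these states.

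**3. Would any other provision catch a change?**

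| Provision | What it does | Would it detect a new drug, a substance-use change or an uneventful pregnancy? |
|---|---|---|
| 7.2 | Permits discontinuation for a new exclusion | No; it acts once the change is known |
| 8.3.4 | Asks about AEs and SAEs at each visit | Only if the change comes with an adverse event |
| 10.1.6, safety monitoring | Monitors adverse effects before and after each TMS and MRI session | No |
| 10.1.6, MRI screening | Screens for MRI contraindications at first contact and on arrival for MRI | No; both precede stimulation |
| 5.4 | Allows rescreening; examples are sleep and hair products | No step is set for these exclusions |
| 5.2 | Asks about pregnancy | No timing given there; 8.3.9 places it at screening |
| 6.5 | Not applicable | No medication is tracked |

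None of these is an eligibility check on a stimulation day.

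**The case against.** The strongest reply is that the grid is incomplete in other respects. It has no row for stimulation itself, motor thresholding, the Need for Cognition Scale or the adverse-event enquiry, so a missing row does not prove a missing check. That is fair as far as the grid goes. But those other items are described elsewhere in the text, whereas a stimulation-day re-check is described nowhere, and Sections 8.1 and 8.3.9 place the checks at the first visit and at screening.

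Second, the existing safeguards do some work. Adverse events are defined broadly and asked about at every visit, and a new psychoactive drug will often follow a new illness that this enquiry should surface. This stands, and it narrows the gap to drugs started without a reportable complaint, substance-use changes and pregnancy.

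Third, the gaps can be short: 10 days to Visit 2 by the grid, or one day under Section 4.1. This is also true, but the nominal schedule and the upper limits are equally permitted.

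Fourth, the absolute risk is small. Section 2.3.1 cites about 1 seizure in 89,000 cases. If a case is read as a session, which is an assumption, 120 / 89,000 is about 0.13% for the whole trial. That figure is described for stimulation within limits in carefully screened people, so it does not apply directly to someone whose status has changed; but only an unknown, probably small, fraction would change. This limits the severity of the point without removing it.

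Fifth, the consensus TMS guidelines that the protocol follows may already call for session-day checks. That cannot be judged from the protocol, which states no such check.

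On the statistical side the objection largely succeeds. Same-session pre-stimulation baselines absorb part of the noise in the EEG measures, and the blinded, pseudo-randomised order makes systematic bias unlikely.

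**Conclusion.** The concern holds and should be fixed. As written, the plan stimulates participants on medication, substance-use and pregnancy information that is nominally 62 to 76 days old and may be about four months old, while naming screening as one of the key protections against seizure. Section 7.2 shows that eligibility is expected to change, but no scheduled step would reveal the change. The re-check is missing at 120 active sessions for seizure risk and at 90 TMS visits for pregnancy, assuming full enrolment of 60 participants, 30 of them women, who complete all sessions.

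How many participants would be affected cannot be derived from the protocol, and the absolute seizure risk is low in a healthy young sample. The case therefore rests on a safeguard the protocol relies on and does not maintain, not on an estimated number of harms. The effect on the efficacy comparisons is a minor matter of added noise.

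**What to change.** Add one row to Section 1.3, marked at Visits 2, 3 and 4 and completed before stimulation. It should repeat the medication and substance-use items of the existing screening form and the pregnancy question, with the test in Section 8.3.9 offered on the same terms. Record any change since the last visit on the CRF, and replace the not-applicable entry in Section 6.5 with a sentence describing that recording. Handle positive answers under the existing rules in Sections 5.2, 7.2 and 8.3.9.

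The cost is a few minutes per visit with questions that already exist. The downside is an occasional postponed session or withdrawal, which the protocol's own exclusions would call for if the change were known. The design, sample size and analysis do not change.

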## 2 INTRODUCTION

### 2.1 STUDY RATIONALE

The healthy human brain is a complex, dynamical system which is hypothesized to lie near a phase transition at rest – at the boundary between order and chaos. Proximity to this critical point is functionally adaptive as it affords maximal flexibility, dynamic range, and information handling capacity, with implications for cognitive control. Divergence from this critical point has become correlated with diverse forms of psychopathology and neuropathy suggesting that distance from a critical point is both a potential biomarker of disorder and a target for intervention in disordered brains. We have further hypothesized that subjective cognitive effort is a reflection of divergence from criticality induced by engagement with demanding tasks.

A key control parameter determining distance from criticality in a resting brain is hypothesized to be the balance of cortical excitation to inhibition (the “E/I balance”). Transcranial magnetic stimulation is a widely used experimental and clinical tool for neuromodulation and theta-burst stimulation (TBS) protocols are thought to modulate the E/I balance. Here we test whether we can systematically modulate cortical dynamics away from the critical point with continuous theta-burst stimulation (cTBS) or intermittent theta-burst stimulation (iTBS), which are thought to decrease and increase E/I balance, respectively, and which should, thereby, impact on cognitive control and subjective cognitive effort during performance of the control demanding tasks.

